Different approaches to the programme are being tested: 1) texts targeted at the student, 2) texts targeted at a study supporter, e.g. a parent or peer identified by the student, or 3) texts targeted at both. The quantitative analysis will estimate the effect size of each intervention compared to the single "business-as-usual" control group. The primary outcome will be the percentage of students that pass their GCSE mathematics or English resit exams after one year (the subject they are receiving texts about). Students' attendance will be considered as a secondary outcome measure.

Study design

POPULATION AND ELIGIBILITY CRITERIA

The intervention is being delivered in further education (FE) colleges in England. FE colleges were selected for the trial because they contain the highest proportion of post-16 students resitting GCSE English and/or maths.

Young people are eligible to take part in the trial if they are:

- Aged 16 or older
- Enrolled at one of the participating colleges in September 2017
- Due to resit GCSE maths and/or English in the 2017/18 academic year.

The developer (BIT) used a targeted recruitment strategy to engage FE colleges with the intervention. An initial screening call was used to gauge colleges' interest and ascertain important information, such as the number of students eligible for the trial. A Memorandum of Understanding (MOU) was sent to interested colleges to sign. The MOU included an overview of the intervention and details

¹ Groot et al. (2017) 'I get by with a little help from my friends Two field experiments on social support and attendance in further education colleges in the UK', http://38r8om2xjhh125mw24492dir.wpengine.netdna-cdn.com/wp-content/uploads/2017/04/Study-Supporter-WP_April-2017.pdf [Accessed 02/11/2017]

² Miller et al. (2016) *Texting Parents: Evaluation report and executive summary*, available at: https://educationendowmentfoundation.org.uk/public/files/Projects/Evaluation_Reports/Texting_Parents.pdf [Accessed 02/11/2017]

³ Kraft, M. A. and Rogers, T. (2015) 'The underutilized potential of teacher-to-parent communications: Evidence from a field experiment', *Economics of Education Review*, 47, pp. 49-63.

⁴ The total number of colleges deviates from the trial protocol (n=32). One college, which had previously been counted as an independent unit, has since been identified as being part of a wider group (i.e. a separate campus rather than separate college).

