⁵ Maths students have one additional exam, and therefore receive an additional reminder text.

about the requirements for participating colleges. College leaders were asked to give their consent and return a signed copy of the MOU to the developer.

Students were recruited to the intervention in September and October 2017 using an online survey provided to college 'project leads' by the Behavioural Insights Team. The survey included information about 'Texting Students and Study Supporters' ('Project SUCCESS') and what would be expected of participants, so that they were able to give informed consent. The survey also included a small number of questions about students' attitudes towards learning and their motivation to study. Students willing to take part were asked to nominate a named study supporter, describe their relationship and provide their study supporters' contact details. Study supporters were not asked to give their consent to take part in the trial, but were able to opt-out of the intervention when the first text message was sent (in early November 2017).

TRIAL DESIGN/ DESCRIPTION OF TRIAL ARMS

Project SUCCESS is being evaluated using a four-armed cluster randomised controlled trial (RCT) with randomisation to each of the four trial arms at the individual level. Clustering within colleges will be accounted for as a fixed effect in the model. The four arms of the trial are:

- Student receives text messages
- Study supporter receives text messages
- Student and study supporter receive text messages
- Control (no text messages)

SAMPLE SIZE

The trial is being conducted in 31 FE colleges.⁶ An average of 123 eligible students per college have given their informed consent to participate in the trial; a total of 3,823 individuals. Students retaking both maths and English have been assigned at random to either the maths or English strand of the intervention, so that approximately 50 per cent are participating in each stand.

NUMBER AND TIMING OF MEASUREMENT POINTS

There will be a single post-intervention measurement point. GCSE resit attainment in maths and English post-treatment will be taken from the National Pupil Database (NPD) in autumn 2018 for all students who participated in the programme in the 2017/18 academic year. Students retaking both English and maths will be randomly assigned to receive texts about just one of these subjects and the primary outcome will be attainment in the subject the student received texts about.

Randomisation

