A multi-site randomisation design was used, with the FE college as the stratifying variable. Students were randomly allocated on a 1:1:1:1 basis to one of four intervention groups (three treatment and one control). It had been agreed at the outset that students retaking both English and maths would receive texts about one subject only. Therefore those students retaking both were randomly allocated to either one or the other outcome group to ensure an overall balanced design, giving an overall average of 31 students per trial arm per college (15/16 per arm, per subject), i.e. an average of 123 students per FE college.

Focusing the design on one subject per person from those taking dual re-sits protects the analysis from potential spill-over effects. For example, a person receiving an English text treatment reminder might also act upon that reminder to do further work on their maths. If that person's maths exam results were included in the non-texting control group this spill-over reminder effect could bias the impact estimate. By allocating dual resit students either to maths or English and removing their results

⁶ Please see footnote 4 for an explanation of how and why this number deviates from the trial protocol.

on the unallocated subject from the analysis, any spill-over effects on the unallocated subject will not be included in the analysis and so cannot influence the results.

Randomisation to each of the four treatment groups was carried out in Stata MP Version 14, using the `.randomise` command with a maximum of 100 randomisations used to achieve balance on the subject taken. The randomisation was conducted at the end of October 2017 by an independent analyst within the evaluation team. Table 1 provides a breakdown of numbers randomised by college and trial arm.

Table 1: Results of the randomisation

College ⁷	Arm 1	Arm 2	Arm 3	Arm 4	Total English	Total maths	Total per college
College 1	51	51	52	51	104	101	205
College 2	8	8	8	9	22	11	33
College 3	18	18	17	18	49	22	71
College 4	8	9	9	9	15	20	35
College 5	42	43	43	43	84	87	171
College 6	22	22	22	22	45	43	88
College 7	26	26	26	25	67	36	103
College 8	33	33	33	32	44	87	131
College 9	23	23	23	24	80	13	93
College 10	29	28	29	28	53	61	114
College 11	33	32	32	32	51	78	129
College 12	6	6	6	6	14	10	24
College 13	50	49	49	49	77	120	197
College 14	27	28	27	27	19	90	109
College 15	22	22	22	22	58	30	88
College 16	51	51	51	52	147	58	205
College 17	13	13	13	13	19	33	52
College 18	16	16	16	15	27	36	63

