²² The NPD does contain semi-continuous scores (from 1-9) for GCSE maths and English resit students. However, students retaking exams as part of the new requirement are likely to be at a very similar academic level, thus likely to obtain results which cluster around the same two or three grades (3-5). We therefore feel there is very limited value in using these grades.

Secondary outcomes

Students' records of attendance will be collected from colleges directly using a secure data transfer; (datasets being shared via secure Natcen's File Transfer Protocol (FTP) site). This will be a simple attendance record stating whether students were present or absent for each class. This will allow for the creation of a variable recording the overall attendance rate, i.e. the proportion of classes attended to all classes given for the course (i.e. attendance at each class taken as a binary variable), for each pupil in the study.

Data on student aspirations, confidence and attitudes to learning will be recorded as part of the process evaluation and does not constitute part of the impact evaluation.

Analysis

Primary intention-to-treat (ITT) analysis

It is proposed to run an intention-to-treat analysis, with a binomial outcome defined as passes in the numerator and failures and no shows in the denominator, as described above. This will involve running separate models for each of the three paired outcomes, i.e. each treatment group compared separately to the control group, where the significance level of the test will be conducted using the adjusted Bonferroni level. We propose to use a binomial multilevel logistic regression model, with students at Level 1 nested within colleges at Level 2, and colleges will be allowed to vary randomly, with a residual mean centred at zero with a Gaussian distribution.

The basic form of the model is:

$$\text{logit}(\pi)_{ij} = \beta_{0j} + \beta_{1j}\text{treatment}_{ij} + r_j \quad (2)$$

We will run separate models for each treatment comparison group as follows:

$$\text{logit}(\pi)_{ij} = \beta_{0j} + \beta_{1j}\text{treatment}_{ij} + r_j \quad (\text{Treatment} = \text{Student text only})$$

$$\text{logit}(\pi)_{ij} = \beta_{0j} + \beta_{1j}\text{treatment}_{ij} + r_j \quad (\text{Treatment} = \text{Supporter text only})$$

$$\text{logit}(\pi)_{ij} = \beta_{0j} + \beta_{1j}\text{treatment}_{ij} + r_j \quad (\text{Treatment} = \text{Student and Supporter text jointly})$$

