Where the outcome variable is regressed onto the treatment binary indicator. All analyses will be conducted using the Stata analysis package.

The analysis does not adjust for academic achievement at baseline due to the lack of available data (see footnote 17).

Imbalance at baseline for analysed groups

Randomisation, if conducted correctly, should result in equivalent distributions of characteristics in the treatment and control groups. Any such differences arising will do so by chance. We will explore the potential for chance imbalances first through an inspection of the descriptive statistics of various characteristics, comparing treatment and control groups. Secondly, we will run a statistical model to identify any characteristics associated with any imbalance.

The NPD data received as standard in an NPD extract (i.e. data from Tiers 1 and 2, e.g. age, gender, everFSM) can be used to predict imbalances in the treatment and control group through regressing the treatment/control binary indicator onto the suite of extracted NPD variables. We propose to explore this using the model form (2) above with the logit transform, as described in the text. Any coefficients found to be significant will indicate imbalance and these variables will be included in an extension of model (2) above as a sensitivity test on the impact effect; i.e. we will extend model (2)

with significant predictors from the imbalance model and compare the magnitude of the impact estimate between the two impact estimate models.

Missing data

Based on past experience we anticipate missingness to be relatively low for the outcome variables. Missingness is of concern primarily if the variables with missing data are (i) related to the outcome and (ii) the pattern of missingness differs between treatment and control groups. If variables with missing values are unrelated to outcomes then there is no need to adjust for them. Such an adjustment will not reduce bias but will likely decrease precision through increasing the variance of the impact estimator, either through weighting or imputation variance adjustments.

If variables with missingness relate to outcomes, but the pattern of missingness is the same between treatment and control groups, again there is no need to adjust for missingness. The key concern is whether missingness is related to outcomes and whether the pattern of missingness differs between the treatment and control groups.

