We also note that potentially we can extend the compliance estimator using the distribution of the proportion of compliance to create separate 'groups' for each level of compliance (e.g. group 1 = compliance < 25%, 2 = 50% etc.). If we have sufficient numbers in each group, we could calculate an 'average causal response with treatment intensity' (ACLTI) (Angrist and Pischke, 2009, Section 4.5.3).²⁸ This approach uses two-stage least squares to weight together the estimates across the compliance groups. We will update the analysis plan accordingly should the distribution of non-compliance²⁹ allow for a reasonable estimation of ACLTI.

Secondary outcome analyses

We originally proposed in the protocol to analyse attendance in class as a continuous outcome defined as the proportion of classes attended out of the total number taught. On reflection, it seems

²⁵ Accounting for No-Shows in Experimental Evaluation Designs
<https://doi.org/10.1177/0193841X8400800205>

²⁶ Identification and Estimation of Local Average Treatment Effects
<http://www.nber.org/papers/t0118>

²⁷ In principle, it is possible that people send themselves weekly text reminders which are similar to those used in the experiment but we will not know that from our design.

²⁸ Angrist, J. D., & Pischke, J. (2009). *Mostly harmless econometrics: An empiricist's companion*. Princeton: Princeton University Press.

²⁹ We will not know the full extent of non-compliance, i.e. drop out/bounce-back until the end of the experiment because people can drop out at any time.

more appropriate to consider this as a binomial outcome because the binomial distribution will bound predicted proportions between unity and zero. In other words, attendance at each session will be treated as a binary outcome (attended/not attended). We will use a logit model to explore the proportion of sessions attended versus the total number of sessions. In addition, we will amend the proposed CACE analysis to be appropriate to a binary outcome (see below). Therefore, analysis of the secondary outcomes takes the same form as model 2, where $\pi_i = \frac{Y_i}{X_i}$, where X is the total number of classes and Y is the total number of classes attended, i.e.

$$\text{logit}(\pi)_{ij} = \beta_{0j} + \beta_{1j}\text{treatment}_{ij} + r_j \text{ (Treatment = Student text only)}$$

$$\text{logit}(\pi)_{ij} = \beta_{0j} + \beta_{1j}\text{treatment}_{ij} + r_j \text{ (Treatment = Supporter text only)}$$

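### The attendance outcome counts classes held before randomisation and the first text, which pulls the estimated effect towards zero and leaves early attendance unused as a covariate

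*SAP*

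**What the plan says.** Under Outcome measures, Secondary outcomes, the SAP builds one attendance rate per student: "the proportion of classes attended to all classes given for the course". The source is a class-level record from each college: "This will be a simple attendance record stating whether students were present or absent for each class". The section Secondary outcome analyses carries the same definition into the model, "where X is the total number of classes and Y is the total number of classes attended". Neither section gives a date from which classes count.

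The timeline is set elsewhere in the SAP:

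- Eligibility (Study design): "Enrolled at one of the participating colleges in September 2017".
- Recruitment (Study design): "Students were recruited to the intervention in September and October 2017".
- Allocation (Randomisation): "The randomisation was conducted at the end of October 2017".
- Start of texting (Study design, on the supporters' chance to opt out): "when the first text message was sent (in early November 2017".

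The attendance models take the form of model (2), which contains treatment and a random college effect only. Of that model the SAP says: "Where the outcome variable is regressed onto the treatment binary indicator". The lack of baseline adjustment is explained by the lack of data on prior academic achievement (Primary intention-to-treat analysis and footnote 17). Attendance before randomisation is not discussed as a possible covariate.

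**The concern.** An outcome window should open when treatment can begin to act. Here it opens at the start of the course, about two months before the first text. Attendance in those weeks is the same in expectation in all four arms, yet it enters both numerator and denominator. The estimated difference is therefore an average of a true effect on later classes and a zero effect on earlier ones.

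The dilution passes into every quantity derived from the intention-to-treat estimate. The relative risk moves towards 1. The treatment-on-the-treated estimate in formula (4) divides the diluted effect by the share receiving texts, so a compliance correction does not undo it.

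The early classes are also the natural baseline for this outcome. They precede allocation, they come from the same record, and they should predict later attendance. The plan folds them into the outcome when they could be used to reduce its variance. Better attendance is a stated aim of the programme, and the introduction cites earlier texting trials that improved it, so a diluted null result could mislead about how the intervention works.

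**Working it through.** **The plan's own figure.** The SAP gives no power or minimum detectable effect for attendance. Its figure for the pass rate reproduces from formula (1) with ω = 0 and no covariates. The multiplier with 30 df is 2.535 + 0.854 = 3.389. Then 3.389 × √(0.9 / (0.25 × 31 × 60)) × √(0.3 × 0.7) = 0.0683, or 6.8 points as in Table 2. This confirms the formula but does not bear on attendance.

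**Inputs.** From the SAP: the definition of the rate, the denominator X, and the dates above. Assumed, because the SAP does not give them: 32 to 38 teaching weeks, 7 to 8 of them before the first text; classes spread evenly over weeks; equal SDs for early and later attendance; early-late correlation r of 0.5 to 0.7.

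**Share of classes before treatment, f.** Smallest 7/38 = 0.184; largest 8/32 = 0.25.

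**Dilution.** Difference over all classes = (1 − f) × difference over later classes. For a true gain of 4 points:

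- f = 0.184: 4 × 0.816 = 3.3 points
- f = 0.25: 4 × 0.75 = 3.0 points

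**Sample size.** With later-class variance set to 1, the whole-course rate has variance V = f² + (1 − f)² + 2f(1 − f)r. The sample needed, relative to an outcome on later classes only, is V / (1 − f)².

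| f | r | V | (1 − f)² | Ratio |
|---|---|---|---|---|
| 0.184 | 0.5 | 0.850 | 0.666 | 1.28 |
| 0.184 | 0.7 | 0.910 | 0.666 | 1.37 |
| 0.22 | 0.5 | 0.828 | 0.608 | 1.36 |
| 0.22 | 0.7 | 0.897 | 0.608 | 1.47 |
| 0.25 | 0.5 | 0.8125 | 0.5625 | 1.44 |
| 0.25 | 0.7 | 0.8875 | 0.5625 | 1.58 |

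**Power.** Suppose the later-classes outcome, unadjusted, had 80% power at the SAP's two-sided 0.0167. The whole-course outcome then has Φ(3.236 × (1 − f)/√V − 2.394). This gives 68% at f = 0.184, r = 0.5, and 57% at f = 0.25, r = 0.7.

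**Gain from the covariate.** In a linear approximation, adjusting later attendance for early attendance multiplies the standard error by √(1 − r²): 0.866 at r = 0.5 and 0.714 at r = 0.7. The 80% reference becomes 91% and 98%. The planned models are logistic, so these two figures indicate the order of the gain and are not a forecast.

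**The case against.** Early classes precede allocation, so including them cannot produce a false effect. A reader might infer that the attendance result would be invalid or biased in favour of texting. The design does not support that: the pull is only towards no effect. Whole-course attendance is also a coherent descriptive quantity, the outcome is secondary, and the SAP makes no power claim for it. All of this stands, and it limits the weight of the point.

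The size depends on a calendar and a correlation that the SAP does not give. That also stands. A reader might take a single sample-size factor of 1/(1 − 0.22)² = 1.64. That holds the SD unchanged, which with equal SDs requires early and later attendance to correlate perfectly. At the same 22% share, r of 0.5 to 0.7 gives 1.36 to 1.47.

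A reader might infer that the trial claims to have no baseline measure at all. It does not. It says that it lacks a usable measure of prior achievement, and it plans an imbalance check on NPD variables with a sensitivity model.

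A reader might also want early attendance in the primary pass models. The documents give no figure for how well it predicts passing. The section Effect size calculation gives a reason to keep those models free of covariates: the relative risk then varies with covariate level. That reason does not defend the attendance window, but it has a practical consequence for the attendance models. Formula (5) uses only the constant and the treatment coefficient, so with an uncentred covariate it would be evaluated at zero early attendance.

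Finally, the SAP promises a record for each class but does not say that classes are dated. A split by date is likely to be feasible, but this is not established.

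**Conclusion.** The point holds for the attendance outcome. The definition and the dates are both in the SAP, no other section limits the window, and the dilution follows by arithmetic. The absolute effect is shrunk by the share of classes before treatment, which is 18% to 25% if 7 to 8 of 32 to 38 weeks precede the first text. The loss of efficiency is equivalent to needing about 1.3 to 1.6 times the sample, given equal SDs and a correlation of 0.5 to 0.7. Confidence is high on the definition, the timeline and the direction, and moderate on the size, which rests wholly on those assumptions. The cost is lost sensitivity and an unused covariate. The primary analysis is untouched. The definition should be changed before the attendance data are analysed.

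**What to change.** - Define Y and X over classes held from one fixed calendar date, the same for all arms: either the randomisation date or the week of the first text. A common date introduces no selection after randomisation.
- Compute each student's attendance rate before that date and enter it as a covariate in the attendance models, with a missing indicator. The SAP already treats missing predictors this way in its missing-data model (footnote 23).
- State how the relative risk is obtained from the adjusted model, either by centring the covariate or by standardising over its distribution.
- Report the whole-course rate as supplementary.
- Leave the primary pass models as they are. If early attendance is used there at all, limit it to a sensitivity analysis.

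The cost is SAP wording, a request that colleges supply class dates, and one more step in the relative-risk calculation. Students who enrolled late will have few or no early classes, so their baseline rate will be noisy or missing.

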- We assume a total of 31 participating colleges and an average of 60 students per college for each of the three pairwise comparisons, with 30 in each treatment arm and 30 in the control (with a broadly even split between maths and English). This means a total of 930 students in each treatment arm and 930 in the control group; a total of 1860 for each of the three pairwise comparisons.
- Maths and English outcomes (i.e. a pass or fail in the English or maths GCSE resit exam) will be considered together as a single outcome variable.
- We assume equal proportions of students in the treatment and control groups ($P = 0.5$) for each pairwise comparison.
- We anticipate a baseline pass rate of 30% ($\theta = 0.3$)
- We have three separate significance tests for the primary outcome, with each of the three treatment groups separately compared to the control group.
- We assume a nominal Type 1 error rate of 0.05 with a two-tailed test, amended using a Bonferroni adjustment for three separate independent tests, to a value of 0.0167 for each test. The Type II error rate is set at 0.2, giving power of 0.8.
- We assume¹⁴ an intra-cluster correlation coefficient (ρ) of 0.1.
- No between site heterogeneity is expected (i.e. $\omega = 0$).
- No level 1 baseline test covariate has been included in the calculation, for reasons explained below. There are also no level 2 stratification variables because we have treated the colleges as random effects and no preliminary stratification was undertaken for college type.
- We assume no attrition in the design, our rationale for which is explained below.
- The EverFSM MDE calculation combined all three treatment arms and assumed a 20% prevalence per college, giving $(90 \times 0.2) + (30 \times 0.2) = 24$ students per college.

The assumptions for each MDE estimation are given in Table 2, below.

The sample size calculations in Table 2 were originally intended to enable the detection of a seven percentage point increase in the GCSE pass rate, from (an estimated) 30 per cent to 37 per cent.¹⁵ However, the underlying model for the purposes of this power calculation, which we have now changed as described above, assumed, a fixed effects model, with no random variation at Level 2, i.e. colleges represented strata from a population fully defined by the sample.

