¹⁸ MDE calculations based on formulas for the calculation of sample sizes for binary outcomes outlined in McConnell and Vera-Hernández (2015) *Going Beyond Simple Sample Size Calculations: a Practitioner's Guide*. IFS Working Paper W15/17. Institute of Fiscal Studies. Available at: <https://www.ifs.org.uk/uploads/publications/wps/WP201517.pdf>

¹⁹ The BIT texting platform allows the developer to monitor the number of 'bounce-backs' (i.e. messages which could not be delivered). This number is available for each weekly 'batch' of text messages sent.

²⁰ It is possible that students may request their data not be used in the experiment. If this happens we will consider treating them as missing data and, if appropriate, apply the weighting strategy described for dealing with missing data.

such events from the primary analysis. Consequently, all students starting the experiment will be included in the analysis under the intention-to-treat estimator.

In addition, students who used their own telephone number when asked to provide contact details for a study supporter²¹ will be included in the group into which they were allocated for treatment. We will address non-compliance through the calculation of causal average complier estimates (see below).

Outcome measures

Primary outcome

Primary outcome: GCSE resit attainment in maths or English post-treatment will be taken from the National Pupil Database (NPD) in autumn 2018 for all students who participated in the programme in the 2017/18 academic year. For those students taking both English and maths we will include only the subject relevant to the group to which they were allocated, i.e. English or maths, as appropriate. We will pool into a single group all students allocated to the maths group with all students allocated to the English group so that the success rate is defined as a pass in English or a pass in Maths. This gives us an average of 30 students in each treatment arm per college: 15 in English and 15 in maths, combined into a single group of 30 students. Consequently, each of the three pairwise analyses will comprise 60 students per college, i.e. 30 in the treatment group and 30 in the control group. Overall, across all three treatments and the control group there are $60 \times 4 = 320$ students on average per college in the experiment.

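### The three primary models leave out subject, the factor the randomisation was repeated to balance; if maths and English pass rates differ, the tests are somewhat conservative

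*SAP*

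**What the plan says.** **Randomisation.** College was the stratifying variable, and the allocation to four arms was run "with a maximum of 100 randomisations used to achieve balance on the subject taken". No criterion for acceptable balance is given, and Table 1 shows totals by subject and totals by arm but not subject by arm.

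**Outcome measures, Primary outcome.** The two exams form one pass/fail variable: "We will pool into a single group all students allocated to the maths group with all students allocated to the English group".

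**Analysis, Primary intention-to-treat (ITT) analysis.** Model (2), fitted once per treatment arm against control, has a treatment term and a random college intercept, and is summed up as "Where the outcome variable is regressed onto the treatment binary indicator". There is no subject term.

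**Reasons given.** The same section explains the absence of baseline attainment by lack of data. The Effect size calculation section regards having no covariates as an advantage, because the relative risk (RR) from a logistic model depends on covariate levels. Neither is a reason specific to subject, which is known for every randomised student.

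**Where else subject could enter.** The baseline-imbalance check adds only National Pupil Database variables that prove significant, and only as a sensitivity analysis. The Subgroup analyses section fits subject and its interaction with treatment, but with all treatment arms combined.

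**The concern.** Subject was a design variable: the allocation was constrained by it. When a factor that predicts the outcome is forced into balance, the variation it causes drops out of the real sampling error of the treatment contrast. A model without that factor still counts the variation as noise. The test statistic then varies less than the model assumes, and the test rejects less often than its nominal level.

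The college effect cannot stand in for subject. In Table 1 the English share runs from 19/109 = 17% (College 14) to 80/93 = 86% (College 9), yet most of the variation in subject lies between students in the same college.

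What is at stake is precision. The trial has no baseline attainment covariate and divides alpha by three, and here a covariate that is already known is left unused.

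**Working it through.** **Inputs from the SAP (Calculation of sample size)**
- Alpha: "We assume a nominal Type 1 error rate of 0.05 with a two-tailed test", then "amended using a Bonferroni adjustment for three separate independent tests, to a value of 0.0167 for each test".
- Power: "The Type II error rate is set at 0.2, giving power of 0.8".
- Control pass rate: "We anticipate a baseline pass rate of 30" per cent, so the variance is 0.3 × 0.7 = 0.21 and the SD 0.458.
- Size: "We assume a total of 31 participating colleges and an average of 60 students per college for each of the three pairwise comparisons", split equally between treatment and control.
- Intra-cluster correlation 0.1, no between-site heterogeneity, no covariates, no attrition.

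**Step 1: reproduce the stated MDE.** Formula (1) with 30 degrees of freedom:
- multiplier = t(1 − 0.0167/2; 30) + t(0.8; 30) = 3.389
- MDE = 3.389 × √[0.9 / (0.25 × 31 × 60)] × 0.458 = 6.83 points

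This matches the stated 6.8. The free-school-meals column also reproduces (10.66 against 10.7).

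**Step 2: how much subject varies within colleges.** From the subject columns of Table 1, Σ(English × maths / total) / Σ total = 0.2295. Against an overall variance of 0.25, that is 92% within colleges. (The printed College 31 row gives 66 students by arm but 61 by subject. The effect here is negligible.)

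**Step 3: share of within-college outcome variance explained by subject.** The SAP gives no pass rates by subject, so the gap d is an assumption, centred on 30%:

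R² = 0.2295 × d² / (0.21 × 0.9)

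**Step 4: consequences.** On the pass-rate scale, by normal approximation except for the MDE, and assuming that subject is fully balanced by arm:
- excess of the standard error without subject = 1/√(1 − R²) − 1
- MDE with subject = 6.83 × √(1 − R²)
- size without subject = 2 × [1 − Φ(2.393/√(1 − R²))]
- power without subject = Φ(0.842/√(1 − R²))
- power with subject = Φ(3.235/√(1 − R²) − 2.393)

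| Assumed gap (rates) | R² | SE excess | MDE with subject | Size without subject | Power without → with |
|---|---|---|---|---|---|
| 0 (30/30) | 0 | 0 | 6.83 | 0.0167 | 80.0% → 80.0% |
| 10 (35/25) | 1.2% | 0.6% | 6.79 | 0.0160 | 80.1% → 80.6% |
| 20 (40/20) | 4.9% | 2.5% | 6.66 | 0.0141 | 80.6% → 82.2% |
| 30 (45/15) | 10.9% | 6.0% | 6.45 | 0.0112 | 81.4% → 85.0% |

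At a 5-point gap the SE excess is 0.15% and the MDE 6.82.

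**Step 5: check by simulation.** Null runs used the Table 1 colleges, subject balanced within college and a linear model with college effects (4,000 runs per gap). At gaps of 10, 20 and 30 points:
- SD of the test statistic without subject: 0.996, 0.973 and 0.941 (the formula √(1 − R²) gives 0.994, 0.975 and 0.944).
- SD with subject: 1.001, 0.996 and 0.992.
- Rejection rates without subject: 0.0170, 0.0148 and 0.0145.
- Rejection rates with subject: 0.0178, 0.0160 and 0.0168.

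The rejection rates have a Monte Carlo error of about √(0.0167 × 0.9833/4,000) = 0.002. They are too noisy to confirm the exact sizes in the table, and the rate at 30 points lies above the formula's 0.0112.

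**Step 6: the log-odds scale.** In a logistic simulation at a 20-point gap (400 runs), adding subject raised the standard error of the treatment coefficient from 0.1012 to 0.1038. The coefficient rose from 0.300 to 0.315, so the mean z statistic went up from 2.96 to 3.03.

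**The case against.** The case for leaving the model alone has several parts.

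- **The harm is conditional.** With equal pass rates nothing is lost, and the SAP gives only a pooled 30%. This stands. The largest figures need a threefold difference between subjects (45% against 15%), which nothing in the document supports.
- **Planned power is intact.** A reader might infer that the trial falls short of its planned power. It does not: the 6.8-point MDE was computed without covariates and reproduces on that basis. Precision is given up only relative to an adjusted model that the plan never assumed.
- **The reported standard error would not shrink.** A reader might infer that the model's standard error is simply too large. For the log-odds coefficient it rises on adjustment. The statement is right only relative to the true sampling variation under forced balance, or on the pass-rate scale.
- **The balance achieved is unknown.** The sizes in the table assume that subject-driven variation is fully removed. The SAP states a ceiling on the number of draws but no acceptance rule, and shows no arm-by-subject counts. The sizes are therefore the most conservative case, not the actual level of the test.
- **There is a stated rationale.** A model without covariates makes the RR easy to compute. That is a convenience, and averaging predictions over the sample answers it. It does mean that the fix reaches beyond model (2).

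None of this supplies a reason to omit subject in particular. The combined-arm interaction model does not replace adjustment in the three primary tests.

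**Conclusion.** The point holds as a mismatch between design and analysis with a modest, conservative effect. A balancing factor, known for every student, is missing from all three primary models without a reason specific to it.

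If maths and English pass rates differ by 10, 20 or 30 points, including subject would bring the MDE from 6.8 to about 6.8, 6.7 or 6.4 points. On the plan's own formula, power would rise by about 0.4, 1.6 or 3.6 points. The size of the test without subject could be as low as about 0.016, 0.014 or 0.011 instead of 0.0167. With no gap nothing changes. These figures rest on assumed gaps, on the plan's 30% pass rate and intra-cluster correlation of 0.1, and, for the sizes and power, on full balance of subject by arm.

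The document does not support any reading of bias, inflated type I error or a shortfall against the planned power. The change is still worth making before results are seen, because adding a covariate afterwards would look selective.

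**What to change.** 1. Prespecify a maths/English indicator as a fixed effect in model (2) for the three primary comparisons, and likewise in the attendance models and the EverFSM-only model.
2. Replace formula (5), which uses only the constant and the treatment coefficient, and revise the related text in the Effect size calculation section. Obtain the RR and the pass-rate difference by averaging predictions over the sample (for example with Stata margins), so that each comparison keeps one trial-wide figure. Say how the college effect is handled in that averaging.
3. State that the odds ratio, which the Non-compliance with intervention section also promises to report, is then conditional on subject.

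The cost is minor rewording, one extra coefficient per model and a slightly different odds-ratio estimand. Subject is known for every randomised student, so no data are lost.
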